**b. Study duration and number of study visits required of research participants.**

Medical oncologist participation in the study will occur throughout the duration of recruitment.

Immediately after providing informed consent, medical oncologists will be asked to complete a one-page survey of socio-demographic characteristics, training, and experiences in the care of persons with breast cancer. Medical oncologists will subsequently complete a brief one-page survey immediately after the visit of participating patients, and a one-page exit survey upon completion of patient recruitment for the study. Patient and family participation in this study will transpire over no longer than 26 weeks, and will involve a screening telephone call to determine eligibility, one in-person encounter at the time of a regularly scheduled physician office visit, and two follow-up telephone calls of approximately 30 minutes duration at 1 weeks (range: 0-3 weeks), 3 months (range: 10-20 weeks) and 9 months (range: 3555 weeks). The in-person encounter is not expected to require more than 45 minutes time beyond the regularly scheduled physician visit. Participants will provide written consent to participate in the study (10 minutes) complete a pre-visit communication tool (10 minutes), and complete a brief post-visit survey (10-15 minutes). The expected duration of the study from the perspective of patient and family participants will proceed over the course of about 16 weeks (but may transpire over a longer period for some participants who are unavailable to complete the follow-up calls at the scheduled 16 week interview); the duration of the study for medical oncologist participants will proceed throughout the course of patient/companion enrollment. The overall study duration is expected to be about 12 months.

**c. Blinding, including justification for blinding or not blinding the trial, if applicable.** This is a single blind, two group randomized trial where the study team will be blinded to group assignment. Outcome measures will be assessed by interviewers masked to treatment assignment and without interventionist contact. Patient/family dyads will not be blinded to group assignment.

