research staff to receive a copy of the patient-family agenda-setting checklist, a clipboard and pen, and instructions describing how to complete the checklist, which they will complete together in the clinic waiting room. Participants who are randomized to the control arm will receive care as usual. Medical oncologists, patients, and families will complete post-visit surveys immediately after the visit. After the visit, patients in the intervention group will meet briefly with research staff to facilitate registration for the EPIC patient portal MyChart, including informational handouts about OpenNotes (as relevant) and MyChart. After the visit, participants in both groups will be offered general breast cancer resource handouts that are available to all breast cancer patients at the Johns Hopkins SKCCC. Patients and families will complete baseline, 3-month and 9-month follow-up telephone interviews by a research assistant who is blind to assignment status. Telephone interviews will be audio recorded for quality control purposes. Patients who decline audio recording will not be excluded from the study. Medical oncologists will complete an exit interview upon completion of patient recruitment.

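### Does the claim in 4.c that the study team is blinded undermine the outcome data, given that staff deliver the intervention and doctors supply one secondary outcome?

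*Combined protocol and SAP*

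**What the plan says.** Section 4.c makes three statements on masking. The first covers everyone on the research side: "This is a single blind, two group randomized trial where the study team will be blinded to group assignment". The second covers assessment: "Outcome measures will be assessed by interviewers masked to treatment assignment and without interventionist contact". The third says openly that patients and family members know their arm. The oncologists are not mentioned.

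Section 4.a describes who does what. Intervention dyads meet "research staff to receive a copy of the patient-family agenda-setting checklist, a clipboard and pen, and instructions describing how to complete the checklist". Later, "After the visit, patients in the intervention group will meet briefly with research staff to facilitate registration for the EPIC patient portal MyChart". Neither step happens in the control arm.

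Data are collected in three ways:

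- **Telephone:** "Patients and families will complete baseline, 3-month and 9-month follow-up telephone interviews by a research assistant who is blind to assignment status".
- **Visit day:** "Medical oncologists, patients, and families will complete post-visit surveys immediately after the visit". Section 4.b repeats this for the doctors: "Medical oncologists will subsequently complete a brief one-page survey immediately after the visit of participating patients".
- **End of recruitment:** "Medical oncologists will complete an exit interview upon completion of patient recruitment".

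Section 7.a places the four primary outcomes at 3 and 9 months, reported by patients and family members. Section 7.b lists the secondary process measures, among them the doctor's view of how effective the family member was in the visit, without naming an instrument or time point. Section 7.c plans no inferential tests and intends effect sizes to feed the planning of a larger trial.

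**The concern.** The blinding statement is wider than the procedures. Anyone who hands a dyad the checklist or helps with portal registration knows that the dyad is in the intervention arm, so the study team as a whole cannot be blinded.

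The sentence on masked assessment also reads as if it covered every outcome measure, yet a masked assessor is described only for telephone calls with patients and families. Oncologists take no part in those calls. Their rating of the family member most probably comes from the survey after each visit, for which no masking is described. Section 8.d adds that research staff help patients complete surveys, and nothing excludes the person who delivered the checklist.

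At stake are the effect sizes carried forward from this pilot. A doctor who knew the arm might rate intervention families more generously, and the larger trial could then be planned on an inflated difference. Randomization stratified by doctor tends to even out lenient and strict raters across arms. It does not remove a tendency of the same doctor to rate the two arms differently.

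**Working it through.** The plan gives no figure to reproduce, and no standard deviation, target effect or error rate from which a bias could be sized. The check is a comparison of text, followed by a count of the outcomes affected.

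**Step 1: who must know the arm.**

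| Role | Task (section) | Masking status |
|---|---|---|
| Staff giving checklist and portal help | Intervention arm only (4.a) | Unmasked by necessity |
| Telephone research assistant | Baseline, 3-month and 9-month calls (4.a) | Stated to be masked |
| Patients and family members | Respondents (4.c) | Stated to be unmasked |
| Oncologists | Survey after each visit, exit contact (4.a, 4.b) | Not stated |

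The first row contradicts "This is a single blind, two group randomized trial where the study team will be blinded to group assignment" if that sentence is read alone.

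**Step 2: whether 4.c misleads when read whole.** The following sentence requires interviewers to be "Outcome measures will be assessed by interviewers masked to treatment assignment and without interventionist contact" in the sense of having no dealings with the interventionists. A rule that separates assessors from interventionists makes sense only if the interventionists know the arm. Section 4.a then identifies the masked person, the telephone research assistant. The operative rule is therefore clear, and the fault lies in the two words naming the study team.

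**Step 3: primary outcomes.** Section 7.a names four: illness understanding, family satisfaction with cancer care, self-efficacy and anxiety. All are set at 3 and 9 months. The only patient and family contacts described at those times are the masked calls. Primary outcomes without interviewer masking: 0 of 4.

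**Step 4: secondary outcomes.** Section 7.b lists:

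- family effectiveness in the visit, reported by patient and by doctor: 2
- satisfaction with the doctor, reported by patient and by family: 2
- quality of communication, reporter not named: 1

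Total: 2 + 2 + 1 = 5 reports. One of the 5, the doctor's, comes from a respondent who is never telephoned. For the other 4 the source is not given; they could come from the masked calls or from the visit-day surveys.

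**Step 5: what kind of masking the doctor's report could have.** A one-page survey completed by the doctor has no interviewer to mask. The open question is whether the respondent knows the arm, which is a different matter from assessor masking. The documents do not say that doctors learn the arm, nor that they do not.

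**Step 6: what the results are used for.** Section 7.c reports the consistency, direction and size of differences, tests no hypothesis and sets no decision threshold. No conclusion in the plan depends on the doctor's report being masked.

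**The case for a change.** The strongest opposing case rests on the doctor's report. Section 3.a describes the team's earlier checklist study, in which doctors' post-visit ratings of families differed by 94.1 − 60.0 = 34.1 percentage points between arms. A measure of that kind could well influence the planning of the next trial, and 4.c taken at face value implies that it is collected under masking. A few words would correct the impression.

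Most of this stands as description. The phrase in 4.c is too wide, the oncologists' status is omitted, and the source of the secondary outcomes is not written down. What does not follow is that the data or their reading would change. Narrowing the phrase alters no procedure. Which form supplied each secondary outcome will be evident from the completed forms, and a competent report would present a doctor-completed survey as just that. That this rating comes from the visit-day survey is itself an inference, though a sound one: the doctor's only other contacts are one survey after consent and one after recruitment ends.

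A rule barring whoever delivered the checklist from helping with the patient's post-visit survey is not clearly an improvement. It argues from silence in a privacy paragraph. Such a person exists only in the intervention arm, so the rule could make survey help and missing items differ between arms, or require another staff member on the day; the documents give no staffing numbers. The gain would be limited in any case, since the patients know their own arm. The sequence in 4.a already suggests that the post-visit survey comes before portal registration.

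**Conclusion.** No change to the plan is needed. The statement about the study team is a slip of wording that 4.c itself largely corrects. The oncologists' masking status and the source of the secondary measures are gaps that analysts can fill sensibly when they report.

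The size is small: 0 of 4 primary outcomes lose interviewer masking, and 1 of 5 secondary reports is clearly outside the masked calls. That report is a process measure in a pilot without inferential testing, and no amount of bias is shown.

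The conclusion rests on three assumptions. The 3- and 9-month primary outcomes are collected in the masked calls, as their timing implies. The interviewers are in practice kept apart from the interventionists, as 4.c requires. Effect sizes from visit-day surveys are read with the caution that 7.c asks for. Interviewer masking does not remove the influence of patients and families knowing their own arm, but 4.c discloses that openly.

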**d. Justification of why participants will not receive routine care or will have current therapy stopped.**

Not applicable. This is a study of a behavioral intervention to improve communication.

**e. Justification for inclusion of a placebo or non-treatment group.**

We will undertake a single blind, two group randomized trial to estimate the potential effects of the intervention on outcomes for patients with breast cancer and their family caregivers. The strategies that are being proposed are low cost, already exist, have been designed to minimize impact on clinical workflow, and are readily transferrable to other provider systems. The study will examine the effects of the intervention protocol on communication outcomes, as well as provide evidence of its acceptability in mainstream medical oncology practice that would support broader diffusion. For these reasons, the control group protocol will comprise usual care which is in this case existing clinical practice.

**f. Definition of treatment failure or participant removal criteria.**

Not applicable. This is a study of a behavioral intervention to improve communication.

**g. Description of what happens to participants receiving therapy when study ends or if a participant's participation in the study ends prematurely.**

Not applicable/relevant. Participation in the study is voluntary. This is a study of a behavioral intervention to improve communication.

## 5. Inclusion/Exclusion Criteria

Participants of this study will include three groups: (1) medical oncology patients, (2) family members (broadly defined), and (3) medical oncologists. Inclusion/exclusion criteria for each of these groups are as follows:

- A. Medical oncology patients. Inclusion criteria: established patient of participating medical oncologist greater than 18 years of age, have a diagnosis of early stage or advanced breast cancer, are receiving active systemic therapy (in the form of IV adjuvant systemic therapy if early stage), are English speaking, able to provide informed consent themselves, and identify a family member who they would like to include in their care. Exclusion criteria: younger than 18 years, pregnant, not being treated for breast cancer, do not attend medical visits with family member or unpaid friend or unwilling for their family member or unpaid friend to be contacted.
- B. Family. Inclusion criteria: Family member (spouse, adult child, parent, adult sibling) or unpaid friend who accompanies patient to medical visits. Exclusion criteria: paid non-family member.
- C. Medical oncologist. Inclusion criteria: practicing medical oncologist at a participating clinic who provides care to patients with breast cancer.

## 6. Drugs/ Substances/ Devices

- a. **The rationale for choosing the drug and dose or for choosing the device to be used.**  
Not applicable
- b. **Justification and safety information if FDA approved drugs will be administered for nonFDA approved indications or if doses or routes of administration or participant populations are changed.**  
Not applicable
- c. **Justification and safety information if non-FDA approved drugs without an IND will be administered.**  
Not applicable

## 7. Study Statistics

### a. Primary outcome variable.

We will assess a comprehensive set of process measures and outcomes that correspond to the efficacy and implementation potential of the intervention. We will assess clinical efficacy of the intervention by examining communication processes and outcomes. Implementation measures will be assessed from practice-based metrics relating to infrastructure, resources, and clinician and staff time and effort for intervention start-up and delivery. Clinical efficacy measures have been selected based on the following criteria: 1.) known reliability and validity, 2.) sensitivity to change, 3.) clinical relevance to quality of life, 4.) reflection of objective indicators of the domains we seek to impact, and 5.) psychometric properties of instruments balanced with practical considerations relating to respondent burden. Efficacy measures will be derived from survey responses provided by patients, families, primary care providers, health and service utilization from the patient's electronic medical record, and date and time-stamped records of MyChart interactions. Our four primary outcomes will be assessed at 3 months and 9 months on the basis of patient and family caregiver surveys. These outcomes include: patient and family illness understanding, family satisfaction with cancer care, patient and family self-efficacy in managing patient care, and symptoms of anxiety.

Patient and family illness understanding will be measured from four items that assess knowledge that is considered to be essential to making informed treatment decisions in serious illness, including: 1.) understanding of illness, 2.) knowledge of disease status, 3.) awareness of disease state, and 4.) expectation of duration of life (months, years, or decades).(1) Each item will be coded 1 or 0 to reflect the presence or absence of each element of illness understanding. We will use scoring that is adapted to reflect patient stage of disease. These four items will be

summed to construct a summary score (range: 0-4) that reflects illness understanding. This measure has been found to be responsive to communication with oncologists.(1)

Family satisfaction with cancer care will be measured with the short-form 10-item version of the FAMCARE, a validated instrument that was developed to assess family perspective on cancer care.(2, 3) Respondents are asked to rate 10 items that relate to emotional support, personalization of care, support of decision-making, accessibility, and coordination. Response categories include “very satisfied” (2 points), “satisfied” (1 point), or “not satisfied” (0 points), and the 10-items may be summed to yield a total score (range: 0 to 20) with higher scores reflecting greater satisfaction. The internal reliability coefficient of the 10-item FAMCARE is 0.94 across varied age, gender, education, ethnic, and relationship groups. The FAMCARE is responsive to change and has been widely used to support findings of the benefit of interventions to improve the quality of cancer care.

Self-efficacy refers to the extent that patients(4, 5) and families(6-9) are equipped to manage their experiences with care and enact the patient’s care plan. Following measurement conventions(5) questions will begin with the phrase “how certain are you right now that you can ...” and respondents will be asked to place themselves on a 10-point scale ranging from 1 (not at all certain) to 10 (very certain). We will ask patients and families to report their self-efficacy for engaging in tasks related to managing patient care that include managing health information and communicating with patients’ health care providers. The scale is scored by calculating the mean of all items; higher scores reflect greater confidence. Prior work finds self-efficacy is inversely associated with anxiety and stress, positively associated with behavioral outcomes including physical and mental health, and responsive to change.(10)

Anxiety will be measured using the Generalized Anxiety Disorder 7-item (GAD-7) scale, a well-established 7-item instrument that asks about symptoms of anxiety in a two-week recall period from 0 (“not at all”) to 3 (“nearly every day”).

**b. Secondary outcome variables.**

Secondary outcomes involve the following process measures: patient and doctor reports of family effectiveness in visit communication, patient and family satisfaction with the doctor, and reported quality of communication.

**c. Statistical plan including sample size justification and interim data analysis.** In this two-group randomized pilot trial, we will compare the effects of the intervention in the investigational arm on communication and outcomes for up to 70 patients (35 per group) with (a) advanced (stage IV) or (b) early (stage I-III) breast cancer (if receiving IV adjuvant systemic therapy) and their family member. As a Stage 1 developmental study of a complex behavioral intervention, the sample size is based on pragmatic considerations related to available resources, project duration, and study objectives. Analyses will be performed in SAS statistical software, with each patient-family dyad as the unit of analysis. We will rely on established cut-points and approaches to constructing outcome measures, as well as measures of patient and family attributes that will serve as control variables (sociodemographic characteristics, health status, aspects of the patient and family relationship, family role appraisal). We will stratify the study sample based on AJCC TNM staging (stage I-III or stage IV). We will primarily evaluate the consistency, direction, and magnitude of differences in study outcomes by undertaking analyses that are stratified by treatment group (intervention versus control arm) and for subgroups of patients by cancer stage (early or advanced stage). We will evaluate recruitment, retention, and the timeliness and completeness of collected data, as well as intervention acceptability (utility, burden, helpfulness) using questions from our formative work. We recognize the need for caution in interpreting pilot trial results. Therefore, inferential statistical testing is not planned in analyses of the pilot trial. However, we will evaluate recruitment and dropout rate as well as effect size of primary and secondary

outcomes to help inform the design and sample size calculations for a larger trial. **d. Early stopping rules.** None.

## 8. Risks

- a. **Medical risks, listing all procedures, their major and minor risks and expected frequency.** The risks of participating in this study involve inconvenience, personal time, the potential for becoming upset, psychologically stressed or fatigued, and potential loss of confidentiality. There may be some inconvenience to patients and families associated with arriving to a scheduled oncology visit earlier than otherwise necessary and staying later to complete a survey. There are risks associated with a breach of confidentiality. Subjects may experience discomfort discussing health or worries. Family members who screen positive for depressive symptoms (on the basis of PHQ-2 scores  $\geq 3$  at follow-up) or anxiety (on the basis of Generalized Anxiety Disorder scores of  $\geq 10$ ) will receive oral notification of this finding and will be asked if they would like to be mailed an educational brochure about depression or anxiety (as appropriate) and options for treatment. Companions will be encouraged to follow-up with their health care provider.
- b. **Steps taken to minimize the risks.**  
Participants will be instructed that participation in the study is completely voluntary and that they may decide to stop at any time. They will be informed of the length and nature of participation. Protection of participant information and audio recordings of telephone interviews will be a key responsibility of study staff. Information from participants will be reported anonymously. All participant surveys, consent forms, and other records containing participant identifiers will be kept in a locked file cabinet. Data will be password protected; only study personnel will have access to identifying information. Redacted (deidentified) versions of the data collection sheets will be used for coding and analysis. No personal identifiers will be included in the analytic database.
- c. **Plan for reporting unanticipated problems or study deviations.**  
This is a study of communication in breast cancer care. The study will evaluate a multicomponent intervention for patients with breast cancer and their family caregivers – each of the intervention components has been successfully tested and found to be acceptable. Adverse events that result from this study are unlikely. Unanticipated problems or adverse events will be reported promptly to the IRB by the PI. Study deviations will be documented and monitored in keeping with Good Clinical Practice in Social and Behavioral Research.
- d. **Legal risks such as the risks that would be associated with breach of confidentiality.**  
Participant privacy will be ensured by asking sensitive questions by telephone so that others who are present at the time of the survey are unable to hear the questions that are being asked. Research staff will assist patient participants in completing study surveys and questions that are asked in person will not involve sensitive topics. Pre-consultation consent and post-visit surveys for patients and family participants will typically be completed in a private room proximal to the clinic waiting room for additional privacy. Information collected from patients and families will not be shared with one another.

e. **Financial risks to the participants.** None

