### 2. Objectives

We will conduct a two-group randomized pilot trial of a multicomponent communication intervention to strengthen communication and longitudinal partnerships among up to 70 patients being actively treated for

breast cancer (early or advanced stage) and their family “caregiver” in an academic medical oncology clinic at Johns Hopkins. The intervention arm comprises: 1.) a patient-family agenda-setting checklist to be completed immediately before a routinely scheduled medical oncology visit, 2.) facilitated registration for the provider-sponsored patient portal (for the patient *and* family member, as desired by the patient), and 3.) education (as relevant) on access to doctor’s electronic visit notes. The control arm comprises usual medical oncology care. We will compare the intervention arm and a control arm of usual care with respect to patient and family-reported outcomes at 3 months and 9 months. We expect that patients and families who receive the intervention will engage in more frequent, higher quality communication with each other and medical oncology providers, and that 3 months and 9 months after enrollment patients and families will have a greater understanding of the patient’s illness, higher self-efficacy with respect to their ability to manage the patient’s care, and that families will be more highly satisfied with the quality of cancer care as compared with participants who receive a control arm of usual care. We will secondarily assess the effects of the intervention on patient and family symptoms of anxiety at 3 months and 9 months.

3. **Background:** This study will evaluate the feasibility of delivering a multicomponent communication intervention in the outpatient setting comprising: 1.) a patient-family agenda-setting checklist completed immediately before a regularly scheduled medical oncology visit, 2.) facilitated registration for the patient portal (for patient *and* family member, as desired by the patient), and 3.) education (as relevant) on access to doctor’s electronic visit notes. In the text that follows we summarize available evidence regarding each of the three intervention components.

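### Section 8.a gives a response to an anxiety score of 10 or more for family members only, although patient anxiety is also a trial outcome

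*Combined protocol and SAP*

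**What the plan says.** Section 8.a (Medical risks) describes the risks of taking part in terms that cover everyone: "Subjects may experience discomfort discussing health or worries". It then sets out an action triggered by a score. The action is for "Family members who screen positive for depressive symptoms" (PHQ-2 of 3 or more at follow-up) "or anxiety (on the basis of Generalized Anxiety Disorder scores of" 10 or more). They are told of the finding orally and asked whether they want a brochure on the condition and its treatment. The step ends: "Companions will be encouraged to follow-up with their health care provider".

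Elsewhere, anxiety is an outcome for both members of the dyad. Section 2 (Objectives) states: "We will secondarily assess the effects of the intervention on patient and family symptoms of anxiety at 3 months and 9 months". Section 7.a lists symptoms of anxiety among the primary outcomes and adds: "Our four primary outcomes will be assessed at 3 months and 9 months on the basis of patient and family caregiver surveys". The instrument is given there too: "Anxiety will be measured using the Generalized Anxiety Disorder 7-item (GAD-7) scale". Section 4.a describes the data collection: "Patients and families will complete baseline, 3-month and 9-month follow-up telephone interviews by a research assistant who is blind to assignment status".

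**The concern.** The sponsor has decided that a score of 10 or more warrants telling the respondent and pointing them to help. Section 8.a applies that decision to one of the two groups whose anxiety is measured. The group left out is the one with breast cancer and on systemic treatment. An interviewer who obtains such a score from a patient finds no action for it in the protocol text, and two interviewers could handle it differently.

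What is at stake is participant protection and consistent conduct, not inference. The missing step is small: oral notice, an optional brochure and general advice.

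**Working it through.** The question is whether text is present or absent, so no formula applies. The check sets the relevant sections side by side.

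1. **Who is covered by the score-triggered step?** In 8.a the subject of the main sentence is family members, and the closing sentence refers to companions. Patients appear in neither.

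2. **Is patient anxiety measured?** Section 2 names patient and family anxiety at 3 and 9 months. Section 7.a takes the primary outcomes, anxiety among them, from patient and family caregiver surveys. The two sections differ on whether anxiety is secondary or primary, but patient anxiety is an outcome under either.

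3. **With which instrument?** Section 7.a names the GAD-7 and no other anxiety measure. No sentence says outright that patients complete it. That follows from steps 2 and 3 together with Section 4.a, under which patients and family members both take the telephone interviews. The inference is strong, but it remains an inference. Section 8.a refers to Generalized Anxiety Disorder scores without repeating the name GAD-7, and I read the two as the same instrument.

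4. **Does any other provision cover a patient's score?** Section 8.b deals with voluntary participation and data protection. Section 8.c sends unanticipated problems and adverse events to the IRB, but sets no score as a trigger and no action towards the participant. Sections 8.d and 8.e concern privacy and financial risk. Section 4.f declares removal criteria not applicable. None of these is a response to a GAD-7 result, and none passes the score to the treating team.

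5. **Does the same gap exist for depression?** No text says that patients complete the PHQ-2. The point is therefore confined to anxiety.

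6. **Size.** Sections 1 and 7.c give up to 35 patients per arm, so 2 × 35 = 70 patients at most fall outside the stated step. That is the whole patient sample, not a measure of impact. The relevant number is the patients who score 10 or more, and the documents give no rate from which to compute it.

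**The case against.** Three arguments on the other side deserve weight.

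**The step may exist elsewhere.** The consent pages were removed from the file, and the interview scripts were not available. A distress procedure for patients would sit naturally in either. This stands as a limit on certainty. A reader might infer that the trial has no safeguard for anxious patients, and the documents do not support that. They support only the narrower statement that 8.a, which is present, names family members alone and points to no patient provision.

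**The difference may be deliberate.** Section 1 says that family members are not formally assessed in care delivery, while Section 5 requires patients to be established with a participating oncologist. The study might be the only party to notice a family member's distress. This is a plausible reason, but 8.a does not give it. Being in oncology care also does not make a research score known to the patient or the clinic: a research assistant collects it by telephone, and 8.b restricts identifying information to study personnel.

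**Acting on the score touches an outcome.** Section 4.e defines the control arm as existing clinical practice, and a notice after the 3-month call could influence anxiety at 9 months. This stands as a cost. It does not defeat the change, because the plan already accepts the same effect for family members, whose anxiety and self-efficacy are also outcomes.

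A reader might also infer that the omission biases the comparison between arms. It does not: the step is absent for patients in both arms alike.

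**Conclusion.** The point holds in a limited form. As written, 8.a would leave a patient scoring 10 or more without the notice that the protocol considers warranted for a family member with the same score, and nothing else in the available text fills the gap. Extending the step is a cheap improvement with a modest safety gain. No estimate, sample size or analysis depends on it.

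The conclusion rests on two assumptions: that patients complete the GAD-7, and that no patient step is set out in the consent form or interview script. If the second is wrong, the remedy shrinks to a cross-reference. The number of patients affected is unknown, and no rate is claimed.

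**What to change.** Extend the anxiety step in 8.a to patients in both arms, adapting the text already there. For example:

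*Patients and family members in either arm who score 10 or more on the GAD-7 will be told of the result by the interviewer, offered a mailed brochure on anxiety and its treatment, and advised to contact their health care provider.*

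Keep the PHQ-2 step for family members only. If a patient step already exists in the consent form or interview script, cite it in 8.a instead. If patients are excluded on purpose, give the reason there.

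The proposed wording does not send the score to the oncology team. That leaves the clinic uninformed unless the patient raises the result, but it keeps the departure from usual care small in the control arm.

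**Cost.** The change needs an edit to 8.a, an interviewer script update and a check that the brochure suits people in cancer treatment. Notice after the 3-month interview could slightly affect 9-month anxiety and self-efficacy in both arms. If the GAD-7 is also given at baseline, which the text does not say, 3-month outcomes could be touched too. The absence of inferential testing does not remove this cost, because Section 7.c intends the effect sizes to inform a larger trial. A simple log of notifications would show how often the step was used. It is optional, and it should carry no arm assignment so that interviewers stay masked.
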